#### *Injection Procedure Description:*

The posterior aspect of the shoulder will be prepped in a sterile fashion with chlorhexidine scrub. The anatomic shoulder landmarks will be palpated under sterile conditions and using a standard posterior shoulder portal a subacromial injection will be given. For those subjects in which subacromial injection would be appropriate (i.e. rotator cuff disease) a 20 gauge needle is inserted posteriorly along the posterior border of the acromion, once contact is made with the underlying bone the needle is slid beneath the acromion and directed to the anterolateral aspect of the subacromial space then injection medication delivered. Dosages for each of the three group assignments will be as follows: Group 1 (control): 5 cc 0.25% Marcaine without epinephrine; Group 2 (ketorolac): 3 cc 0.25% Marcaine without epinephrine and 2 cc Ketorolac 30 mg/ml; Group 3 (kenalog): 4 cc 0.25% Marcaine without epinephrine and 1 cc kenalog.

The Research Team will prepare the appropriate injection medication according to group assignment and the syringe contents will be masked from the physician. Each injection will contain a total of 5 cc.

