#### *Follow-up Interviews*

Subjects will be contacted by phone to obtain VAS score at day 2, and weeks, 1, 2, and 4 after the injection. They will be instructed to return to clinic at routine follow-up intervals at 6 and 12 weeks after the injection and will again be asked to complete the Outcome Shoulder Questionnaire containing VAS, ASES, SF-12, PSQI scores. Subjects range of motion and shoulder strength will also be collected. All data collected with regards to this study will be kept in a password-protected database, which will only be accessible, by study investigators and the research team.

Study subjects who do not respond to the follow-up phone calls in a timely manner, will be mailed a paper copy of the Follow-up Outcome Shoulder Questionnaire and/or emailed a website link to the same questionnaire on [www.surveymonkey.com](http://www.surveymonkey.com)

	Baseline Shoulder Questionnaire			Follow-up					
	Med Record Review	Pre-Injection	5 Minutes Post Injection	Day 2	Week 1	Week 2	Week 4	Week 6	Week 12
Visual Analog Score (VAS)		X	X	X	X	X	X	X	X
American Shoulder and Elbow Score (ASES)		X						X	X
Single Assessment Numeric Evaluation (SANE)		X	X					X	X

Pittsburgh Sleep Quality Index		X					X	X
SF-12		X					X	X
Range of Motion		X	X				X	X
Dynamometer measurements		X	X				X	X
Pt Characteristics	X							
Injury Characteristics	X							
Co-Morbidities	X							
Pt Hx	X							
Meds	X							
Demographics	X							

4.3 Each phone follow-up should take approximately 10 minutes each and the standard follow-up visits should each take approximately 30 to 45 minutes.

4.4 At each time frame, the subjects will be asked to complete a questionnaire. Blood and tissue samples will not be collected for this study.

4.5 Subjects will be billed for the services received whether they participate in the study or not.

4.6 The only change in clinic practice of shoulder disorders as part of this study protocol will be the randomization of injection medication they will be receiving. Subjects will be prescribed physical therapy as is standard for the treatment of shoulder disorders.

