## **9. RECRUITMENT METHODS and CONSENTING PROCESS:**

### *9.1 Screening*

The treating physicians will identify potentially eligible subjects from the UT Southwestern Ambulatory Outpatient Orthopaedic Surgery clinic and John Hopkins clinics: Johns Hopkins Orthopaedics, Johns Hopkins Community Physicians, and Southern Maryland Orthopaedic and Sports Medicine Division of Centers for Advanced Orthopaedics. Study Investigators and their research teams will assess subjects for the study and include a review of the medical record to ensure none of the study exclusion criteria are met. The study will be discussed with potentially eligible subjects.

*9.2 Recruitment:* Only those presenting for a shoulder evaluation at the UT Southwestern Ambulatory Outpatient Orthopaedic Surgery clinic and John Hopkins clinics: Johns Hopkins Orthopaedics, Johns Hopkins Community Physicians, and Southern Maryland Orthopaedic and Sports Medicine Division of Centers for Advanced Orthopaedics, who meet inclusion criteria will be recruited for potential participation in the study.

Informed consent will be obtained prior to initiation of the study. The physician will be involved in the consent conversation. The conversation will be initiated by the research team and physician together. The consent process will involve a dialogue. Specifically, patients and their families will be provided with a pamphlet describing the study, the risks and benefits of participation and what will be expected of them if they choose to participate.

Consent must be obtained from the patient in this study; no legally authorized representatives or surrogates may consent on behalf of the patient. This is due to the subjective nature of assessing pain. All recruitment materials will be provided in English.

9.3 Screening, enrollment, and informed consent process will take place in a private treatment area.

9.4 If a patient decides to withdraw from the study, he/she may do so at any point by informing the Principal Investigator in writing. A 'Note to File' must be inserted into the patient's chart and research file stating the patient formally withdrew from the study with the reason (if given). The patient will be assured that the medical care which they receive will not be affected should they elect to discontinue participation in the study.

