## **14. Biostatistics**

14.1 Statistical Analysis: The specific purpose of this study is to provide descriptive statistics for both the primary and secondary outcomes. Unpaired t or chi-square tests on all pre-op demographic data. The dependent variables will be analyzed by repeated measure of variance to determine if statistically significant differences exist at follow-up assessment. To protect against Type I error, Tukey tests will be used to ensure the alpha levels ( $p < 0.05$ ) will not be falsely declared significant. This is a prospective double-blinded randomized trial. The investigator of the study and examiner who provides the injection will be blind to which group assignment has been provided. Patients will not be told of the injection type. The billing department will create a study account which will allow billing subjects, for the ketorolac or kenalog, without their knowing which injection they received.

14.2 Sample Size: We are planning a study of a continuous response variable from independent control and experimental subjects with 1 control(s) per experimental subject. In a previous study the response within each subject group was normally distributed with standard deviation 23. If the true difference in the experimental and control means is 12, we will need to study 59 experimental subjects and 59 control subjects to be able to reject the null hypothesis that the population means of the experimental and control groups are equal with probability (power) 0.8 for each diagnostic category of rotator cuff tendinopathy, small to medium rotator cuff tears, and large rotator cuff tear arthropathies. The Type I error probability associated with this test of this null hypothesis is 0.05. To account for a 15% drop out rate we will recruit 66 subjects for each of the 3 arms of the trial in each of the 2 diagnostic categories for a total of 400 patients.

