Randomization: Subjects will be recruited from the UT Southwestern Orthopaedic Surgery Clinic and John Hopkins clinics: Johns Hopkins Orthopaedics, Johns Hopkins Community Physicians, and Southern Maryland Orthopaedic and Sports Medicine Division of Centers for Advanced Orthopaedics, from patients who meet the inclusion criteria. As this study design will be prospective randomized double-blinded, we will utilize computer generated block randomization technique. After identifying a patient who meets the inclusion criteria by history, physical examination, and obtaining informed consent, HIPPA, health screen, and baseline measurements, subjects will be randomized into one of three cohorts: 1) Control (Marcaine injection), 2) NSAID injection (ketorolac & Marcaine injection), or 3) Steroid injection (kenalog & Marcaine injection). To ensure that the number of subjects is about the same in the three arms of the study, the randomization scheme will assign patients in a 1:1:1 ratio in randomly permuted blocks of assignments stratified by clinical center. Block size will be determined randomly and the patient will be the unit of randomization.

Enrollment and randomization results will be documented in the patient's chart according to protocol. The randomization allocation will be blinded to both the patient (initially) as well as the physician performing the injection and the investigator conducting statistical analysis of the results. Given the nature of this study looking at the effects of this intervention on multiple shoulder pathologies we anticipate approximately 200 subjects per diagnostic category would be needed for enrollment and complete follow-up.

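### Randomization is stratified by clinical center, but the repeated-measures comparison in section 14.1 names no center term, so the between-arm test at follow-up may lose some power

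*Combined protocol and SAP*

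**What the plan says.** The Randomization paragraph of section 14 states that "the randomization scheme will assign patients in a 1:1:1 ratio", using "randomly permuted blocks of assignments stratified by clinical center". Center is the only stratification factor named. Recruitment is at UT Southwestern and at "John Hopkins clinics: Johns Hopkins Orthopaedics, Johns Hopkins Community Physicians, and Southern Maryland Orthopaedic and Sports Medicine Division of Centers for Advanced Orthopaedics". That reads as four clinics, although the number of strata is not stated.

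Section 14.1 gives the whole efficacy analysis: "The dependent variables will be analyzed by repeated measure of variance to determine if statistically significant differences exist at follow-up assessment", with Tukey tests for multiplicity. It lists no model factors or covariates, and no other section adds a center or site term. The sample-size calculation in 14.2 is a plain comparison of two means, made separately for each diagnostic category. Diagnostic category is not a stratification factor.

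**The concern.** Blocking within center balances the arms inside each center, so center differences largely drop out of the arm contrast. An error term without center still contains them. The estimated standard error is then larger than the true one, and the precision that the blocking bought is not used.

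There are reasons why centers might differ. The clinics are of several kinds and more than one physician is involved ("The treating physicians will identify potentially eligible subjects"). The injection is guided by palpation ("The anatomic shoulder landmarks will be palpated under sterile conditions and using a standard posterior shoulder portal a subacromial injection will be given"), and co-treatment is routine care ("Subjects will be prescribed physical therapy as is standard for the treatment of shoulder disorders"). At stake are wider confidence intervals and a modest loss of power. There is also a decision left open: because 14.1 does not write the model down, center could be put in or left out after the data are seen.

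**Working it through.** **Inputs from 14.2.** Difference 12, SD 23, alpha 0.05, power 0.8, 59 evaluable per arm per diagnostic category.

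**The plan's own figure.** The two-sided normal approximation gives 58 per arm. The t distribution gives 59, with power 0.802. The stated 59 is reproduced, and it is two-sided (one-sided would give 46).

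**Assumptions.** The documents give no between-center variance. Let ρ be the share of outcome variance due to center, taken as 0.05, 0.10 and 0.20. SD 23 is first taken to include site variation. The test is a single two-arm comparison at one follow-up time, by normal approximation.

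**Signal.** The standard error is 23 × √(2/59) = 4.235, and 12/4.235 = 2.834.

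**How much center variance stays in the contrast.** If the analysed patients were fully balanced by center, none would stay, and the true variance would be (1 − ρ) times the naive variance. The calculation in 14.2 is per diagnostic category, however, and blocks are formed by center only. If each category is half of every center, about half the center variance stays in the contrast. The true variance is then (1 − ρ) + ρ/2 = 1 − ρ/2 times the naive variance.

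**Formulas.**
- Real type I error, unadjusted, within a category: 2Φ(−1.96/√(1 − ρ/2))
- Power, unadjusted, within a category: Φ((2.834 − 1.96)/√(1 − ρ/2))
- Power, center in the model: Φ(2.834/√(1 − ρ) − 1.96)

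| ρ | Type I error, unadjusted | Power, unadjusted | Power, with center |
|---|---|---|---|
| 0.05 | 0.047 | 0.812 | 0.828 |
| 0.10 | 0.044 | 0.815 | 0.848 |
| 0.20 | 0.039 | 0.821 | 0.887 |

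Example at ρ = 0.10: 1.96/√0.95 = 2.011, which gives 0.044; 0.874/√0.95 = 0.897, which gives 0.815; 2.834/√0.90 − 1.96 = 1.027, which gives 0.848.

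The last column is slightly optimistic, because it ignores the degrees of freedom spent and the chance imbalance of arms by center within a category.

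**Full balance, for comparison.** Replacing ρ/2 by ρ gives type I errors of 0.044, 0.039 and 0.028 and unadjusted power of 0.815, 0.821 and 0.836. A simulation with full balance (four unequal centers, blocks of 3 or 6, 177 subjects, 4,000 runs; all assumed) gave power without and with center of 0.805 and 0.821, 0.818 and 0.846, and 0.823 and 0.875. Adjusted type I error stayed between 0.049 and 0.053.

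**Small center share.** At ρ = 0.02, under full balance, power is 0.811 without center and 0.817 with it.

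**If SD 23 is within-site only.** Under full balance, unadjusted power is Φ(2.834 − 1.96/√(1 − ρ)) = 0.795, 0.779 and 0.740, against 0.809 with center. The levels are lower, but the loss (about 1, 3 and 7 points) is of similar size.

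**The case against.** **The premises are partly inference.** A reader might infer that the documents show clinics differing in technique and therapy, or that the plan treats center as a known source of difference. They do not. One injection technique is described for all sites. Physical therapy is called standard for the disorder, and co-treatment is left to physician discretion without being tied to site. The stated purpose of the randomization scheme is similar numbers per arm. This objection stands: between-center variation is plausible but assumed.

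**The effect depends on the term tested.** A site shift that is constant over time cancels from a group-by-time test, and 14.1 does not say which term it will test. This stands as a limit. The point applies to the between-arm test, and 14.1 does speak of differences at follow-up.

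**The calculation is not the planned analysis.** It is a single two-arm test, not a repeated-measures analysis with Tukey comparisons. With the Tukey critical value for three arms (about 2.364 in place of 1.96) and full balance, power is about 0.69, 0.69 and 0.70 without center and 0.71, 0.73 and 0.79 with it. Overall power is lower, but the direction is the same.

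**The loss may be small.** At a center share of 5% to 10% it is about 2 to 3 points, and near zero nothing is lost. This stands, and it keeps the point at the level of a worthwhile improvement.

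**Conclusion.** The mismatch is real: the one factor used to stratify the randomization does not appear in the stated analysis. If centers differ, the between-arm test at follow-up is somewhat conservative. Under the assumptions above, adding center gains about 2, 3 and 6 to 7 power points at center shares of 5%, 10% and 20%. The unadjusted type I error within a diagnostic category is about 0.047, 0.044 and 0.039. These sizes rest on the assumed center shares and on each category being half of every center.

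Three stronger readings are not supported:
- **Bias or excess false positives.** The omission does neither; the error is on the conservative side.
- **A type I error as low as 0.028.** That needs full center balance in the analysed set, which stratifying by center alone does not give within a category.
- **A deliberate exclusion of center.** Section 14.1 lists no model terms at all, so this is an omission within a broader lack of detail.

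**What to change.** Add to 14.1: *All between-arm models include clinical center (the randomization stratum) as a fixed factor; very small centers are pooled by a rule fixed before unblinding.* Include diagnostic category in any model that pools the categories. State in the same place which term of the repeated-measures model is the test of treatment, since that decides whether center matters to it.

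The cost is a few degrees of freedom (4 − 1 = 3 if each of the four named clinics is a center). No new data are needed, because center must be known in order to randomize.

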### **3. Concise Summary of Project**

**3.1 Study Design:** The proposed study is a three arm, double-blinded, prospective randomized controlled clinical trial with follow-up immediately after the injection and at day 2, and weeks 1, 2, 4, 6, and 12. In this study we will compare the effectiveness of ketorolac compared to corticosteroid.

Ketorolac is an injectable solution which should be stored at 15 C to 30 C (59 F to 86 F) and protected from light. Marcaine (Bupivacaine) should be stored at room temperature, between 20 C to 25 C (68 F to 77 F). And Kenalog (triamcinolone) should be stored at controlled room temperature, 20°–25°C (68°–77°F), avoid freezing and protect from light. Do not refrigerate.[18]

Medications are stored in a locked cabinet at room temperature. The Research Team will prepare the appropriate injection medication according to group assignment at the time of the appointment. Injections will not be prepared beforehand. Injections will be prepared by inserting the syringe into both bottles and drawing the required amount. The syringe contents will be masked from the physician.

**Study Groups:** Subjects being seen for a rotator cuff injury will be randomized into one of three treatment groups pertaining to their pathology. The intervention will begin once the subject has consented and answered the Baseline Outcome Shoulder Questionnaire. The Baseline Outcome Questionnaire consists of the Visual Analog Score, American Shoulder and Elbow Score, Single Assessment Numeric Evaluation, Pittsburgh Sleep Quality Index, SF-12, range of motion and measure the subjects shoulder strength by using a

dynamometer, and questions pertaining to patient characteristics, injury characteristics, co-morbidities, patient history, medications, and demographics.

A dynamometer is a small, hand-held device which the subject presses against. By pressing against the device, it measures the strength of their shoulder.

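### Section 14.1 names repeated-measures ANOVA without a sphericity correction or covariance structure; if correlation decays between the uneven VAS visits, an uncorrected arm-by-time test would exceed its nominal 5%

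*Combined protocol and SAP*

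**What the plan says.** Section 14.1 states the analysis in one sentence: "The dependent variables will be analyzed by repeated measure of variance", so as to detect any significant difference at follow-up. The next sentence supplies the only error control: "To protect against Type I error, Tukey tests will be used to ensure the alpha levels" are kept at 0.05. The section does not say which effect is tested (arm, time or arm by time), which readings enter the model, what covariance is assumed, or whether an epsilon correction or a multivariate test will be used.

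Section 3.4 lists VAS and ASES as primary. Section 3.1 sets "follow-up immediately after the injection and at day 2, and weeks 1, 2, 4, 6, and 12". With the pre-injection reading, the schedule table in section 4 gives eight VAS readings: pre-injection, 5 minutes, day 2, and weeks 1, 2, 4, 6 and 12. ASES has three: pre-injection, week 6 and week 12.

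Section 14.2 sizes the trial on a single comparison of two means, and its error rate belongs to that comparison: "The Type I error probability associated with this test of this null hypothesis is 0.05".

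**The concern.** The classical univariate F-test of arm by time is exact only under sphericity, meaning that all differences between pairs of visits have the same variance. Equal variances with equal correlations are enough for this, though not strictly necessary. Readings minutes or days apart will usually be more alike than readings 6 to 12 weeks apart, which breaks the condition. The uncorrected test then rejects too often even with complete data, so this is separate from missing visits. Tukey's method adjusts for the number of comparisons and does not repair an error term that does not fit the contrast.

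Two results are exposed: a claim that the arms follow different courses over time, and any comparison of change from baseline that borrows the ANOVA's pooled within-subject error. Because 14.1 is silent, the choice between corrected and uncorrected p-values is also left open until the data are in.

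**Working it through.** **1. The plan's own figure.** Inputs from 14.2: "the response within each subject group was normally distributed with standard deviation 23"; "If the true difference in the experimental and control means is 12"; power 0.8; alpha 0.05, taken as two-sided.

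n = 2 × (1.960 + 0.842)² × 23² / 12² = 2 × 7.85 × 529 / 144 ≈ 57.7, so 58 by the normal approximation. The noncentral t gives 59 (power 0.802), which reproduces 14.2. This is a two-mean calculation and involves no repeated-measures test. 66 recruited per arm less 15% leaves 66 × 0.85 ≈ 56. Simulations at 56 and at 59 per arm agree closely.

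**2. Arm-by-time F-test with no arm effect.** Three arms, 59 per arm, complete normal data, k = 8 readings, 8,000 trials per row. Degrees of freedom are 2 × 7 = 14 and 3 × 58 × 7 = 1,218. The departure from sphericity is ε = (tr A)² / [(k − 1) tr(A²)], where A is the double-centred covariance matrix and ε = 1 means sphericity. All correlation patterns are assumptions.

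| Assumed correlation | ε | Uncorrected | Greenhouse-Geisser |
|---|---|---|---|
| Equal, 0.5 | 1.00 | 5.1% | 4.7% |
| Linear fall by visit, 0.65 to 0.35 | 0.82 | 6.0% | 4.5% |
| Calendar decay 0.7 to 0.95 per week (weight 0.7), measurement error 0.3 | 0.73–0.84 | 6.2–7.4% | 4.7–5.1% |
| Stable part 0.3, calendar decay 0.7 per week (weight 0.5), error 0.2 | 0.74 | 7.1% | 4.9% |
| Same, 0.9 per week | 0.75 | 7.8% | 5.5% |
| Decay by visit order, 0.5 | 0.72 | 7.7% | 4.8% |
| Decay by visit order, 0.7 | 0.55 | 9.5% | 5.1% |
| Decay by visit order, 0.9 | 0.40 | 11.6% | 5.0% |

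A run at 56 per arm gave 7.9% to 12.0% for visit-order decay of 0.5 to 0.9, and 6.0% to 7.0% for calendar decay with a stable part and measurement error. The equal-correlation row confirms that the code holds its level. Calendar decay with no measurement error reached 9.9% to 13.6%, but it makes the pre-injection and 5-minute readings almost identical, so I do not rely on it.

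Without the pre-injection and 5-minute readings (k = 6), the calendar models with measurement error give 6.0% to 6.9%, and visit-order decay of 0.5 to 0.9 gives 7.5% to 10.3%.

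**3. What is not affected.** The between-arm main effect rejected 4.5% to 5.4% of the time in every scenario. Tukey comparisons of arms at one visit, using within-cell variance with equal variances across visits, rejected 4.0% to 5.9%. For the three ASES readings, the arm-by-time test gave 4.2% to 7.5% overall, and 5.0% to 5.9% under calendar decay with measurement error.

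**4. Change from baseline on the pooled within-subject error.** With common variance σ², the true variance of a change to visit j is 2σ²(1 − ρ₀ⱼ). The pooled error has expectation σ²(1 − ρ̄), where ρ̄ is the mean between-visit correlation, so the test assumes 2σ²(1 − ρ̄). The variance ratio is R = (1 − ρ₀ⱼ)/(1 − ρ̄), and an unadjusted 5% comparison of two arms rejects with probability 2Φ(−1.96/√R).

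- Visit-order 0.5 (ρ̄ = 0.215). 5 minutes: R = 0.5/0.785 = 0.64, 1.4%. Week 12: R = (1 − 0.5⁷)/0.785 = 1.26, 8.1%.
- Visit-order 0.9 (ρ̄ = 0.741). 5 minutes: R = 0.1/0.259 = 0.39, 0.2%. Week 12: R = (1 − 0.9⁷)/0.259 = 2.01, 16.7%.
- Stable 0.3, calendar 0.9 per week (weight 0.5), error 0.2 (ρ̄ = 0.634). 5 minutes: R = 0.2/0.366 = 0.55, 0.8%. Week 12: R = (1 − 0.3 − 0.5 × 0.9¹²)/0.366 = 1.53, 11.3%.

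Simulation agrees: 0.1% to 1.2% at 5 minutes and 7.5% to 17% at week 12.

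**The case against.** The strongest reply is that 14.1 never names an arm-by-time test. It speaks only of differences at follow-up, and the 0.05 in the plan is attached to Tukey tests and to a two-mean comparison. A reader might infer that the trial's main test of treatment has a false-positive rate of 7% to 12%. The documents do not support that: the tested effect is unstated, and the between-arm main effect keeps its level. This part of the objection stands. What remains is that arm differences that change over follow-up are tested in this framework by arm by time or by visit-level contrasts, and 14.1 rules out neither.

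A second reply is that every size above 5% depends on invented correlations. That also stands. Equal correlation with SDs varying between 0.8 and 1.2 gave only 5.5%, and other choices of calendar decay with measurement error gave 5.3% to 6.8%. Visit-order decay sits badly with uneven spacing, since it treats 5 minutes to day 2 like week 6 to week 12. At 0.5 and 0.7 it implies baseline-to-week-12 correlations of 0.5⁷ = 0.008 and 0.7⁷ = 0.08, which leaves almost no stable patient differences. At 0.9 the implied value is 0.9⁷ = 0.48, so that argument does not dispose of the top figure. The calendar-time figures are still the better guide.

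A third reply is that standard errors at individual visits need not be wrong. A reader might infer that all visit-level tests are distorted. They are not: raw arm comparisons on within-cell error are sound when variances are equal. The distortion applies to change from baseline on the pooled within-subject error, and 14.1 does not say which error term Tukey will use.

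Finally, silence does not exclude a correction, and common software reports one. That is true, and it is a reason to specify the choice now.

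**Conclusion.** The point holds as a conditional one about VAS. Section 14.1 leaves the covariance handling open for up to eight very unevenly spaced readings, and Tukey tests do not fill that gap. If correlation falls with time between visits, an uncorrected univariate arm-by-time test at nominal 5% rejects about 6% to 8% of the time under calendar decay with stable patient differences and measurement error, and up to about 12% under strong decay. Under the same assumptions, change-from-baseline comparisons on the pooled within-subject error fall to about 1% or less at 5 minutes and rise to roughly 8% to 17% at week 12.

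These figures assume complete normal data, equal variances across visits and correlations that the documents do not give. They do not show that the arm main effect, single-visit comparisons on within-cell error, or the ASES analysis is materially wrong. The change is worth making because it is cheap and settles the choice before the data are seen.

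**What to change.** In 14.1, state which VAS readings count as follow-up and name the arm contrast to be tested. Analyse follow-up VAS with a mixed model for repeated measures with unstructured within-subject covariance, and take arm differences and standard errors at each visit from that model. Even with all seven post-injection readings this means 7 × 8 / 2 = 28 covariance parameters, which is workable with 3 × 59 = 177 patients per diagnostic category.

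If ANOVA is kept, test arm by time with Greenhouse-Geisser correction, which brought the rate to between 4.5% and 5.5% in the tabulated scenarios. Do not use the pooled within-subject error for visit-level or change-from-baseline Tukey comparisons.

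The cost is a few lines of text and standard software options, with no new data or patients. The downside is slightly larger p-values for the arm-by-time test.

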#### Full Thickness Rotator Cuff Tear:

Group 1 (control): will receive an injection of 5 cc 0.25% Marcaine without epinephrine

Group 2 (ketorolac): will receive an injection of 3 cc 0.25% Marcaine without epinephrine and 2 cc ketorolac 30 mg/ml

Group 3 (kenalog): 4 cc 0.25% Marcaine without epinephrine and 1 cc triamcinolone.

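### The 0.80 power in 14.2 belongs to one unadjusted two-arm t-test at 59 per arm; it does not allow for the Tukey tests in 14.1, and 66 recruits less 15% leave 56, not 59

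*Combined protocol and SAP*

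**What the plan says.** Section 14.2 sizes one comparison between an experimental and a control group with SD 23. It reads "If the true difference in the experimental and control means is 12", then "we will need to study 59 experimental subjects and 59 control subjects to be able to reject the null hypothesis", with power 0.8 claimed for each diagnostic category. On error it adds: "The Type I error probability associated with this test of this null hypothesis is 0.05". On attrition: "To account for a 15% drop out rate we will recruit 66 subjects for each of the 3 arms of the trial", in each of two diagnostic categories, about 400 patients in all. The Randomization paragraph of section 14 describes the count differently: "we anticipate approximately 200 subjects per diagnostic category would be needed for enrollment and complete follow-up".

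Section 14.1 gives the analysis: "The dependent variables will be analyzed by repeated measure of variance to determine if statistically significant differences exist at follow-up assessment". It follows this with: "To protect against Type I error, Tukey tests will be used to ensure the alpha levels". It does not say which means Tukey compares, at which visit, or which contrast is primary.

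On the arms, section 3 (Study Groups) labels Marcaine alone as control: "Group 1 (control): will receive an injection of 5 cc 0.25% Marcaine without epinephrine". Section 11.1 calls ketorolac the experimental group. Hypothesis 1 in section 1.2 is that ketorolac is more effective than corticosteroid, while the paragraph after 4.6 expects the two to be equivalent for pain relief. Section 3.4 lists two primary outcomes, VAS and ASES.

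**The concern.** The sample size and the analysis describe different tests. Tukey raises the critical value for each pair, so a sample that just reaches 0.80 without adjustment falls below it unless something else reduces the variance. Section 14.2 mentions neither the adjustment nor any offsetting gain. The evaluable number behind the 0.80 is also not what the stated recruitment and dropout deliver.

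A reader would conclude that each diagnostic category has 80% power, and would probably apply this to ketorolac against triamcinolone because that is the stated hypothesis. If the true power for that comparison is lower, a non-significant result is more likely than the plan implies. Given the sponsor's expectation of equivalence, such a result could be misread as showing it.

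**Working it through.** **Inputs.** From 14.2: difference 12, SD 23, type I error 0.05, 59 per arm, 66 recruited per arm, 15% dropout. From the Randomization paragraph: three arms, 1:1:1. Sidedness is not stated; two-sided is taken because the null is equality of means and a one-sided test would need only 46 per arm (normal approximation).

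**1. Reproduce the plan's figure.** Standard error = SD × √(2/n); noncentrality = difference / standard error.
- n = 59: 23 × √(2/59) = 4.235; 12/4.235 = 2.834. With 116 df the critical t is 1.981 and power is 0.802.
- n = 58: power is 0.796.

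So 59 is the smallest n that reaches 0.80 with a single unadjusted two-sample t-test. There is no room in it for multiplicity.

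**2. Dropout.**
- 66 × 0.85 = 56.1 evaluable.
- 1 − 59/66 = 10.6%, the largest loss that 66 recruits can bear and still leave 59.
- 59/0.85 = 69.4, so 70 recruits would be needed at 15% loss.
- Using 400/6 = 66.7 per arm gives 66.7 × 0.85 = 56.7, with the same conclusion.
- Unadjusted t-test at n = 56: 23 × √(2/56) = 4.347; 12/4.347 = 2.761; power 0.781.

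**3. Tukey over the three arm pairs, one visit, no baseline adjustment** (an assumed family, since 14.1 names none). Critical t = studentized range quantile(0.95; 3 means, 3(n − 1) df) / √2. At n = 59 this is 3.343/√2 = 2.364.

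| Evaluable per arm | Unadjusted t-test | Three-pair Tukey |
|---|---|---|
| 59 (stated) | 0.80 | 0.68 |
| 56 (66 less 15%) | 0.78 | 0.65 |
| 66 (if all recruits complete) | 0.84 | 0.74 |

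Three-pair Tukey reaches 0.80 at 76 evaluable per arm.

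**4. What the model might recover.** The documents give no correlations, so these are assumptions, and 23 is taken as a raw SD.
- Baseline adjustment, SD × √(1 − r²), r = 0.3 to 0.5: three-pair Tukey power 0.70 to 0.79 at 56, and 0.73 to 0.82 at 59.
- Mean of weeks 6 and 12, SD × √((1 + ρ)/2), ρ = 0.7 to 0.5: 0.73 to 0.79 at 56, and 0.76 to 0.82 at 59.
- One pre-named contrast with baseline adjustment, r = 0.3 to 0.5: 0.82 to 0.88 at 56.

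**5. Which pair is powered.** Sections 3 and 11.1 together make experimental against control read as ketorolac against Marcaine. No section justifies a difference of 12 between two active injections. At 56 per arm, one unadjusted contrast, illustrative smaller differences give power 0.63 (difference 10) and 0.45 (difference 8). The 95% CI half-width for one pair is 1.982 × 4.347 = 8.6 points.

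**6. Diagnostic categories.** The figures above assume two categories filled equally. The power sentence in 14.2 names three; with three, 400/9 = 44.4 per arm, and 44.4 × 0.85 leaves about 38. Randomization is stratified only by clinical center, so the number per arm within a category is not fixed by design.

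**The case against.** The best defence is that the 0.65 to 0.68 range is one scenario. Section 14.1 plans repeated measures, and with a favourable correlation three-pair Tukey power reaches 0.82 at 59, above the claim. A single pre-named contrast adjusted for baseline would exceed 0.80 even at 56. This stands: a reader might infer that the trial is underpowered at 0.65, and the documents do not establish that. But they do not support 0.80 for the planned analysis either, because 14.2 gives no correlation, does not say whether 23 is a raw or change-score SD, and claims no gain from the model.

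It can also be said that the dropout error is small and the counts are approximate. Both are true: alone it moves power from 0.80 to 0.78. If the Randomization paragraph means completers, 66 per arm would restore the unadjusted figure (0.84), but three-pair Tukey would still give 0.74 without baseline adjustment.

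A reader might also infer that the two primary outcomes inflate the false-positive rate. That holds only if success on either suffices, which the documents do not say. In that case the rate at one visit with one Tukey family per outcome would be 1 − 0.95² = 9.75% for uncorrelated outcomes, and less with positive correlation. If both must succeed there is no inflation.

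Finally, 14.1 describes its purpose as descriptive. The same section nonetheless plans significance tests with type I protection, and 14.2 claims power.

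**Conclusion.** The point holds in this form: the 0.80 in 14.2 is correct for one unadjusted two-sided two-arm t-test with 59 evaluable per arm, and is not shown for the analysis in 14.1 or for the numbers that the recruitment plan delivers. Under three-pair Tukey at one visit without baseline adjustment, power is 0.68 at 59 and 0.65 at 56. The Tukey mismatch is the larger loss; the dropout error is minor but plain arithmetic. These values rest on that assumed family, on 12 and 23 as stated, and on two categories filled equally.

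It would go too far to say that 14.2 points to no pair at all, since the labels in sections 3 and 11.1 indicate ketorolac against Marcaine. The gap is between that pair and Hypothesis 1, with a further conflict between Hypothesis 1 and the expectation of equivalence after 4.6. This should be fixed before analysis; it does not invalidate the design.

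**What to change.** 1. In 14.2, correct the dropout statement: 66 recruits per arm at 15% loss leave about 56 evaluable, assuming two diagnostic categories filled equally. Reconcile this with the Randomization paragraph (recruits or completers) and with the three categories in the 14.2 power sentence.
2. Restate power for the analysis actually planned. At 56 per arm without baseline adjustment it is about 0.65 if all three pairs are tested with Tukey at one visit, or about 0.78 if one pre-named contrast is tested at 0.05. If the model adjusts for baseline, state the assumed correlation and whether 23 is a raw or change-score SD, and give power for that model.
3. In 14.1 and 14.2, name the outcome, visit and arm pair that 12 and 23 describe, and the Tukey family. Reconcile the powered pair with Hypothesis 1 and with the expectation of equivalence. Do not attach the power figure to ketorolac against triamcinolone unless a difference of 12 is justified for that pair. If one contrast is made primary at 0.05, adjust the remaining two as a separate secondary family.
4. State whether success needs either or both of VAS and ASES. If either, use a fixed testing order or split alpha.
5. Report a non-significant ketorolac against triamcinolone result with its 95% CI (half-width about 8.6 points at 56 per arm, SD 23) and do not call it equivalence.

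Cost: wording only, with no extra patients. The stated power becomes less favourable. Keeping 59 evaluable at 15% loss would instead take 70 recruits per arm, that is (70 − 66) × 6 = 24 more patients over three arms and two categories, and would restore only the unadjusted 0.80.
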